2.1 Primary estimands

An estimand is a precise description of the treatment effect reflecting the clinical question posed by the trial objective. It summarizes at a population-level, what the outcomes would be in the same patients under each of the treatment conditions being compared. Attributes of an estimand include the population, variable (or endpoint) and treatment of interest. It also specifies how intercurrent events are addressed and provides a population-level summary for the variable. The structured framework of estimand detailed in ICH E9 (R1) was newly adopted by the Regulatory Members of the ICH Assembly under Step 4 in Nov-2019.

The clinical question of interest is: What is the difference between IV cipargamin and IV artesunate in early reduction of asexual parasite load in participants with severe *P. falciparum* malaria who are treated with at least one dose of IV treatment?

The justification for targeting this treatment effect is that severe *P. falciparum* malaria is caused by asexual parasite burden, leading to sequestration and microvascular obstruction. Rapid reduction of *P. falciparum* asexual parasites by 12 hours should prevent participants from further deterioration, and so allow eventual recovery from the disease.

The primary estimand is described by the following attributes:

1. Population: Participants with severe *P. falciparum* malaria and who have been treated with at least one dose of IV study medication (either cipargamin or artesunate). Further details about the population are provided in [Section 5](#).
2. Variable: A binary outcome indicating $\geq 90\%$ reduction in *P. falciparum* parasite at 12 hours (H12) after first IV dose as compared to baseline.
3. Treatment of interest: IV cipargamin vs IV artesunate. Further details about cipargamin and artesunate are provided in [Section 6](#).
4. Intercurrent events: (1) taking IV rescue antimalarial medication prior to H12 parasite assessment, or (2) mortality prior to H12 parasite assessment. Details on how to handle the intercurrent event are provided in [Section 12.4.3](#).
5. Summary measure: Difference in proportion of participants with $\geq 90\%$ reduction in baseline parasite count between IV cipargamin dose regimen and IV artesunate will be

evaluated within each cohort separately except Cohort 1, which will be combined with Cohort 2.

2.2 Secondary estimands

The secondary clinical question of interest is: What is the difference between IV cipargamin and IV artesunate in clinical success at 48 hours without the need of IV rescue antimalarial medication?

[figure not shown]
The justification for the secondary estimand is that it will reflect the clinical outcome including recovery from the most severe symptoms of the disease with IV treatment before earliest possible administration of oral antimalarial medication at 48 hours. This objective is being evaluated for possible use in Phase III study. Further details can be found in [Section 12](#).

The secondary estimand is described by the following attributes:

1. Population: participants with severe *P. falciparum* malaria and treated with at least one dose of IV study medication. Further details about the population are provided in [Section 5](#).
2. Variable: A binary outcome indicating clinical success- participant is alive and has absence of asexual parasites and no critical signs of severe malaria (See [Section 8.3.1.2](#) for further details) at 48 hours.
3. Treatment of interest: IV cipargamin vs IV artesunate. Further details about cipargamin and artesunate are provided in [Section 6](#).
4. Intercurrent event: receive IV rescue antimalarial medication before assessing the clinical success prior to H48.
5. Summary measure: Proportion of participants with clinical success with 90% CI within a treatment group as well as the difference between the cipargamin and artesunate treatment group.

3 Study design

Figure 3-1 Study design

Notes:

KAE609 (Cipargamin)

Moderately severe malaria – Prostration and/or repeated vomiting (Barnes et al 2004)

Study to progress from Cohort 1 to Cohort 2 without interruption if none of the KAE609 arms in Cohort 1 meets the stopping criteria.

*Results from Cohort 1 and Cohort 2 will be analyzed to determine the safe and efficacious exposure range and the corresponding doses (KAE dose regimen 3) for participants in Cohorts 3 to 5.

Doses for Cohort 4 will be confirmed after PK analysis from upto 6 KAE609 participants from Cohort 3 and for Cohort 5, it would be post completion of Cohort 4 .

** Cohort 5 recruitment is dependent on availability of adequate toxicology package to dose down to ≥ 6 m

KAE609 doses across the study will be adaptive depending on the safe and efficacious exposure range identified before the study (for Cohorts 1-2) and after interim assessment of Cohort 1 & 2 (for Cohorts 3-5)

This will be an adaptive, multicenter, randomized, open label, sequential cohort study in participants aged ≥ 12 years old in Cohorts 1-2 and < 12 years old to ≥ 6 months in Cohorts 3-5 with a diagnosis of moderately severe and severe *P. falciparum* malaria (Section 16.4). This study is investigating the efficacy (parasite reduction and clinical outcome), safety, tolerability and pharmacokinetics of different injectable dose regimens of cipargamin in comparison to injectable artesunate. Cohort 1 includes only 18 participants aged ≥ 12 years old. As IV cipargamin has not yet been evaluated in patients with severe malaria, this first Cohort includes participants that are diagnosed with moderately severe malaria. Cohort 1 participants will have a minimum parasite count of 60,000 per µl and these high parasitemia levels will help to determine parasite clearance rates for the two dose regimen. In Cohorts 2-5 participants with severe malaria and a minimum parasite count of 5,000 per µl will be enrolled in an age-decreasing manner. This design aims at minimizing risks for pediatric participants < 12 years and at ensuring sufficient number of participants with severe malaria signs to evaluate their clinical improvement in the secondary endpoint. In all cohorts, participants on IV cipargamin arms will receive one daily injection of IV cipargamin over a minimum of 2 days and a maximum of 3 days; with IV artesunate as rescue medication. Participants in the IV artesunate arm will be administered a minimum of 3 doses during the first 2 days of treatment. Participants in all arms will receive Coartem bid for 3 days following IV therapy.

See sections [Section 6.1.1](#), [Section 6.1.2.1](#) and [Section 6.2.1](#) for details of each treatment arm.

Cohorts 1-2:

In Cohorts 1 and 2, 18 and 42 participants ≥ 12 years, who satisfy the inclusion/exclusion criteria will be randomized in the ratio 1:1:1 to one of three treatment arms. :

- IV cipargamin (KAE609) dose regimen 1
- IV cipargamin (KAE609) dose regimen 2
- IV artesunate

The two doses of IV cipargamin for Cohorts 1 and 2 have been selected based on the rationale described in [Section 4.2](#). The doses might be adjusted before the study start based on results obtained from the first in human (FIH) study in healthy volunteers to ensure exposure is maintained within the predicted safe and efficacious range (AUC_{0-24h} of 5-42 $\mu g \cdot hr/ml$) in the study participants.

Cohorts 3-5:

The results from Cohorts 1 and 2 will be analyzed to determine the safe and efficacious exposure range and the corresponding doses (cipargamin (KAE609) dose regimen 3) for the participants in Cohorts 3 to 5. In these Cohorts all participants will be pediatric and below 12 years of age. Only one dose of IV cipargamin will be selected for use in Cohorts 3-5 (see [Section 4.2](#)). For the pediatric participants in Cohorts 3 to 5, a convenient dosing regimen based on weight bands will be defined ([Section 4.2](#)). The results from Cohort 1 and Cohort 2 will be summarized for interim assessment (IA), and the data will be reviewed by an Independent DMC before continuing to dose pediatric participants < 12 years in Cohorts 3-5. The IA will be performed on key efficacy, safety and PK data up to Day 29.

In the age descending Cohorts 3 to 5 the PK exposure will be confirmed in up to 6 participants per cohort treated with IV cipargamin before recruiting remaining participants. PK data obtained from these initial participants from every cohort may lead to modification of the selected dose in order to maintain IV cipargamin exposure within the determined safe and efficacious range. At the same time, recruitment in the subsequent younger age Cohort will be started for the first 6 participants. In case of a need for dose modification in a particular Cohort, additional participants maybe recruited into that cohort to ensure data are available for approximately 38 participants at the selected dose level.

- Cohort 3: Pediatric participants ≥ 6 y - < 12 y
- Cohort 4: Pediatric participants ≥ 2 y - < 6 y
- Cohort 5: Pediatric participants ≥ 6 m - < 2 y

In Cohorts 3 to 5 approximately 192 participants (aged ≥ 6 months to < 12 years) who satisfy the inclusion/exclusion criteria will be randomized in a 1:1 ratio to one of two treatment arms:

- IV cipargamin (KAE609) dose regimen 3
- IV artesunate

Study conduct

Participants will be admitted to the hospital on Day 1 and screened for inclusion in the study. If they meet the eligibility criteria they will be randomized to treatment within 3 hours of

admission. Participants will be hospitalized under close supervision for at least 72 hours after start of IV treatment and until oral treatment with Coartem has been initiated. Hospitalization can be extended, if needed, for participants based on disease signs, until IV treatment has been completed and oral treatment with Coartem has been initiated. All participants should be followed up until Day 29. Visits to assess safety and efficacy will be scheduled during the follow-up period as described in the assessments schedule ([Table 8-1](#), [Table 8-2](#)). If malaria symptoms re-emerge outside the scheduled study visits or any other adverse events occur, participants will be instructed to contact the investigator. Study design and assessments will slightly vary between cohorts, details are captured in [Section 5](#) and [Table 8-1](#), [Table 8-2](#). The safety of the entire study will be monitored by a Data Monitoring Committee (DMC) and stopping criteria (based on safety and lack of efficacy criteria) are in place throughout the study ([Table 3-1](#)). Recruitment in any treatment arms with cipargamin (KAE609) will be paused if stopping criteria are met. In event of recruitment pause, all relevant data will be reviewed in an ad-hoc DMC meeting and the next steps to be taken with the relevant IV cipargamin dose will be decided by Novartis based on the DMC's recommendation. Planned DMCs will occur at the end of Cohort 2 and at the end of Cohort 4. Additional DMC meetings may be conducted depending on the need.

Participants in all cohorts will be closely monitored through parasitological, biochemical, hematology, physical and neurological examinations ([Table 8-1](#), [Table 8-2](#) and [Section 8.3.1](#)). Rich PK sampling will be done in Cohorts 1 - 3 and sparse PK sampling will be done in Cohorts 4-5 for IV cipargamin participants.

Stopping criteria for the study

Data related to participant's efficacy and safety will be continuously monitored by the sponsor. If participants randomized to any IV cipargamin arms meet either the safety criteria or lack of efficacy criteria as listed in [Table 3-1](#) below, the study may be paused and a DMC review conducted.

Table 3-1 Criteria to temporarily pause the recruitment and initiate DMC review

Cohorts with planned recruitment	Number of participants meeting the safety criteria*	Number of participants meeting the lack of efficacy criteria**
Cohort with 6 participants	2	2
Cohort with 14 participants	2	2
Cohort with 20 participants	3	3
Cohort with 38 participants	6	6
Throughout the study (116 participants within a single IV cipargamin treatment arm)	14	14
*Safety criteria - All cause death or SAE possibly related to cipargamin **Lack of efficacy criteria – Use of IV artesunate as rescue medication (as per protocol defined criteria) in participants randomized to IV cipargamin		

4 Rationale

4.1 Rationale for study design

As severe malaria is primarily a disease of young children, children down to 6 months have been included in this clinical study to obtain data in the relevant patient population. In order to ensure adequate efficacy and safety, pediatric participants will be included in an age descending manner with the youngest participant between 6 months and 2 years of age enrolled in the final cohort after IA and DMC.

As IV cipargamin has not yet been evaluated in patients with severe malaria, Cohort 1 will start with a study population, which is less severely ill and ≥ 12 years old. Participants diagnosed with moderately severe malaria and high parasitemia (60,000-250,000 parasites per μl) at baseline and without significant elevations in liver function tests (ALT and total bilirubin, see [Section 5.2](#)) will be randomized to Cohort 1. The selected inclusion criteria should limit the variability of the disease signs of participants included in Cohort 1, while allowing for efficacy assessment based upon parasite clearance and initial safety monitoring. If stopping criteria ([Table 3-1](#) in [Section 3](#)) are not met in any of the IV cipargamin arms in Cohort 1, recruitment of Cohort 2 will be initiated after LPLV (last patient last visit) of Cohort 1. In case of any efficacy/safety concerns identified in Cohort 1, PK data will be analyzed and the following actions could be taken in consultation with the data monitoring committee (DMC):

- Up to six additional participants per treatment arm may be recruited in Cohort 1 before proceeding to Cohort 2
- Dose for Cohort 2 may be modified (increased or decreased) to ensure exposure within the safe and efficacious range

In Cohort 2, participants in the same age population of ≥ 12 years diagnosed with severe malaria ([Section 16.4](#)) will be enrolled. Participants in Cohorts 2 to 5 will be enrolled with parasitemia levels of at least 5,000 parasites per μl . An interim assessment after Cohort 2 will evaluate efficacy, safety and PK results of the two IV cipargamin doses compared to IV artesunate. Based on these results, a safe and efficacious exposure range will be defined for the use in Cohorts 3-5. The dose for Cohorts 3-5 will be selected to ensure that exposure in children < 12 years of age remains within the determined safe and efficacious range.

Parenteral artesunate is the first line treatment for severe malaria as recommended by [WHO 2015](#). All participants will be treated with IV cipargamin or IV artesunate for at least 24 h (minimum of 2 doses of IV cipargamin and 3 doses of IV artesunate) and until oral therapy can be tolerated. IV therapy will be followed by oral antimalarial therapy as per standard treatment practice. The oral treatment is a 3-day course of Coartem to ensure complete elimination of parasites in participants.

The open label design is chosen since the dosing frequency and method of administration of test drug and comparator is not similar. Hence, blinding the treatment would require multiple placebo injections in a double dummy design which is ethically not acceptable considering the severity of the disease and need for inclusion of pediatric participants. Furthermore, the risk of bias arising out of the open-label design is minimized due to the objectivity of the primary endpoint, which is based on reduction of parasitemia.

4.1.1 Rationale for choice of background therapy

Parenteral antimalarial treatment followed by a full course of oral antimalarial therapy is the standard of care for management of parasitemia and achieving cure in severe malaria patients (WHO 2015). In addition, supportive treatment is required to manage severe malaria. Such treatments include but are not limited to blood transfusions, fluid replacement therapy, anticonvulsants and glucose transfusions. Supportive treatment for management of severe malaria will be administered as per local treatment guidelines and will be documented as concomitant medication in the study database. A minimum basic standard of supportive treatment will be maintained across all the sites participating in the study. Participants should not receive any additional antimalarial drug unless used as rescue medication as per protocol.

4.2 Rationale for dose/regimen and duration of treatment

The primary aim of the intravenous antimalarial treatment in severe malaria is a rapid reduction of the initial parasite load. The efficacy of oral cipargamin in terms of parasite clearance has been demonstrated in previous studies using single doses between 10 mg and 150 mg. In study CKAE609A2202, aparasitemia was achieved by as early as 12 hours post-dose in the majority of the subjects treated with a single dose of oral cipargamin of ≥ 25 mg and by 24 hours post-dose in the majority of the subjects treated with oral cipargamin irrespective of dose. CCI

IV artesunate, the standard of care for severe malaria, has reported mean PRR₂₄ values between 7 and 43 across studies (Newton et al 2001, Nealon et al 2002, Newton et al 2003, Maude et al 2014). The CCI from four oral cipargamin studies including more than 150 participants with uncomplicated malaria (CKAE609X2201, CKAE609X2202, CKAE609A2201 and CKAE609A2202) is shown in Figure 4-1. In these studies, participants with baseline parasitemia of up to 60,000 parasites per μ l were included CCI oral cipargamin treatment. The full exposure-response relationship in participants with hyperparasitemia, as expected in severe malaria, remains to be elucidated.

In the same study CKAE609A2202, no safety concerns in patients with uncomplicated malaria were associated with CCI

The doses of IV cipargamin in this study have been selected in order not to exceed these mean exposures from the previous study.

The PK exposures of cipargamin following IV administration were predicted using a population PK model based on preliminary data from the first two cohorts of the ongoing phase 1 study CKAE609X2111. An adjustment in predicted exposures was made CCI (Silamut et al 1991) and the impact of CCI observed in studies in uncomplicated malaria and in healthy volunteers study, CCI CKAE609X2111.

Based on the above criteria, selected doses for Cohorts 1-2, i.e. 20 and 40 mg once every 24 hours, are expected to provide exposures within the safe and efficacious range. Due to the half-life of cipargamin of approximately 24 hours, cipargamin is expected to accumulate with daily

dosing. To limit the total exposure of IV cipargamin in this first study of IV cipargamin in malaria patients, participants will receive a maximum of 3 daily doses. For severe cases, the total duration of IV therapy (either IV cipargamin followed by IV artesunate or IV artesunate alone) will be defined by the medical condition of the participants and the prescribing information of IV artesunate.

Cohorts 1-2

The lowest dose selected for Cohorts 1-2 i.e. 20 mg is expected to CCI [REDACTED] 1 [REDACTED]. As such, this dose is expected to provide equivalent or faster initial parasite clearance than the standard of care i.e. artesunate and thereby minimize the risk for severely ill participants due to slow parasite clearance.

A dose of 40 mg is expected to provide CCI [REDACTED] observed with oral cipargamin in participants with uncomplicated malaria (refer Figure 4-1 below). Hence, a fast parasite clearance rate is expected to be achieved in all the participants and a full dose response curve can be obtained to ensure that the appropriate benefit risk relationship is established in adolescent and adult participants before dosing children below 12 years in Cohorts 3-5. The anticipated exposure with 40 mg dose is comparable to the highest exposure, which was achieved in oral cipargamin in study CKAE609A2202 without any safety issues.

In conclusion, the inclusion of 20 and 40 mg doses in Cohorts 1-2 will cover a wider exposure range and facilitate the selection of an appropriate dose for later Cohorts 3-5.

Cohorts 3-5

A single dose level with the best benefit risk potential will be evaluated in participants < 12 years old based on interim assessment of data from Cohorts 1 and 2. The population PK and / or PBPK model will be developed / up-dated with this data to predict exposures in participants from Cohort 3-5. If required, the speed of IV bolus administration may be adjusted to keep the Cmax within the safe range as determined in Cohorts 1-2. CCI [REDACTED]

[REDACTED]

Figure 4-1

CCI

4.3 Rationale for choice of control drugs (comparator/placebo) or combination drugs

Parenteral artesunate is the WHO recommended first line treatment for severe malaria ([WHO 2015](#)). Three IV doses are given over the first 24 h (0, 12 and 24 h) and then q24h until oral therapy can be tolerated. A full course of oral treatment (artemisinin based combination therapy, Coartem in this study) is given afterwards to ensure elimination of the malaria parasite. Other treatments available for severe malaria are such as IM artesunate, IV quinine and intramuscular artemether. However, these treatments are only recommended when IV artesunate is not available.

4.4 Purpose and timing of interim analyses/design adaptations

An interim assessment (IA) will be performed after completion of Cohort 2. The study team and an independent DMC will review key PK/efficacy/safety data including the proportion of participants with $\geq 90\%$ parasite reduction at 12 hours as well as at 24 and 48 hours and parasite reduction ratios, relevant safety data and PK data from all participants of Cohorts 1 and 2. Based on data from Cohorts 1 and 2, the highest safe and effective exposure will be determined and used to select doses for Cohorts 3-5.

For subsequent Cohorts 3-5, randomization will start with the next descending age group. Novartis pharmacokineticist will review the PK exposure and AAG (if required) in up to 6 participants treated with IV cipargamin. After confirming that the exposures are adequate,

enrollment of participants will continue in the initial cohort (applicable for Cohorts 3-5) and the next lower age cohort will be opened for enrollment. However, enrollment for Cohort 5 will only be initiated post completion of Cohort 4 and a DMC meeting. In case, the dose for a specific age group has to be adjusted, additional participants with the modified dose may be recruited.

Additional IAs may be conducted (for e.g. after Cohort 4) to support decision making concerning the current clinical study, the sponsor's clinical development projects in general, or in case of any safety concerns.

Following dose and design adaptations are permitted in the study as per below [Table 4-1](#):

Table 4-1 Dose and design adaptations permitted in the study

For Cohorts 1-2, CCI	-	Cohort 1	Cohort 2	Interim assessment to identify safe and efficacious exposure range (CCI) for Cohorts 3-5	Cohort 3-5
	Doses	20 mg and 40 mg May be modified before start of study based on IV cipargamin PK data from FIH study	20 mg and 40 mg May be modified based on emerging PK data from Cohort 1 or if one of the IV cipargamin treatment arms meets the stopping criteria		Age and weight band based dose may be modified based on PK data from up to first 6 participants in each of the cohort to achieve adequate exposure identified for Cohorts 3-5
	Sample size	Up to six additional participants per treatment arm may be recruited before proceeding to Cohort 2 if doses selected at start of the study for Cohort 2 are modified	Up to 14 additional participants per treatment arm may be recruited before proceeding to Cohorts 3-5 if IA suggest benefit of using higher exposures in Cohorts 3-5		Additional participants may be recruited in each cohort after dose modification to ensure 38 evaluable participants on the same dose level

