4.5 Risks and benefits

Severe malaria is a medical emergency and is affecting primarily young children in Africa. With currently only one WHO recommended IV treatment, there is considerable medical need for an additional treatment option as injectable antimalarial. Based on the preclinical and clinical evaluation to date, as presented in the [Investigator's Brochure](#), oral cipargamin has been

generally safe and well tolerated. Healthy subjects have been dosed up to single oral doses of 300 mg, and repeated oral doses up to 150 mg q24h for 3 days, and patients up to single oral doses of 150 mg, and repeated oral doses of 50 mg. The participants in this study will be receiving IV cipargamin for the treatment of severe malaria and based on the positive efficacy results with the oral formulation in the treatment of uncomplicated malaria, they are expected to receive benefit from it. The risk to participants (as per [Investigator's Brochure](#)) will be minimized by adherence to the inclusion/exclusion criteria, stopping rules, close clinical monitoring (including multiple laboratory evaluations as per the Assessment Schedule), the staggered design of the study with PK and safety reviews between cohorts. The exposure **CCI** with selected doses of IV cipargamin is not expected to exceed exposures already observed with oral cipargamin.

Cohort 1 of the current study will include participants aged ≥ 12 years suffering from moderately severe malaria accompanied by a high parasite count. Younger participants will only be enrolled in Cohorts 3-5 of the study in descending age order. There will be safety, efficacy and PK assessments after Cohort 2 to confirm the dose for Cohorts 3-5, which will be administered to children aged ≥ 6 months to 12 years. Participants will be hospitalized under close supervision until they are considered fit to be discharged by the investigator. Stopping criteria will be applied as mentioned in [Section 3](#) and all participants will be closely monitored on an ongoing basis. Recruitment in a specific treatment arm can be put on hold, as necessary.

Expected benefits of IV cipargamin

Based on available evidence about rapid parasite reduction with oral cipargamin in uncomplicated malaria, IV cipargamin is also expected to provide rapid parasite reduction in severe malaria patients. Rapid parasite reduction should lead to an improvement in clinical symptoms and overall clinical benefit for the patient.

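### The lead-in gate in Cohorts 3-5 names only a PK check, and the cohort pause count of 6 for Cohorts 3 and 4 cannot act within it short of six events in six children

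*Protocol*

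**What the plan says.** **The gate.** Protocol Section 3 (Cohorts 3-5) says that "the PK exposure will be confirmed in up to 6 participants per cohort treated with IV cipargamin before recruiting remaining participants". Section 4.4 gives the reviewer and the subject of the review: "Novartis pharmacokineticist will review the PK exposure and AAG (if required) in up to" six participants. It then makes release conditional: "After confirming that the exposures are adequate", the cohort continues and the next younger one opens. Section 3 adds: "At the same time, recruitment in the subsequent younger age Cohort will be started for the first 6 participants". In Table 4-1 the entry for Cohorts 3-5 also names PK data only.

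**Cohort 5.** An extra condition applies: "However, enrollment for Cohort 5 will only be initiated post completion of Cohort 4 and a DMC meeting".

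**The numeric pause counts.** Protocol Table 3-1, repeated in SAP Table 2-14, counts deaths from any cause and SAEs possibly related to cipargamin, by planned cohort size. The row "Cohort with 6 participants" has a count of 2, and the row "Cohort with 38 participants" has a count of 6. Cohorts of 14 and 20 have counts of 2 and 3, and the whole regimen of 116 has 14. Section 12.8.2 plans 6, 14, 38, 38 and 20 participants per arm in Cohorts 1 to 5. The six-participant row therefore matches Cohort 1, and no row is assigned to the lead-in groups.

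**Reviews.** Planned DMC meetings fall after Cohort 2 and after Cohort 4 (Protocol Sections 3 and 10.2.4, SAP 2.15.1). Section 4.5 lists among its risk mitigations "the staggered design of the study with PK and safety reviews between cohorts".

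**The concern.** The lead-in treats the first children in a new age group, at a dose scaled from older participants. As written, passing it depends on exposure alone. The numeric count that applies to Cohorts 3 and 4 was calibrated for 38 participants and has almost no power over six. Five deaths or related SAEs among the first six children of Cohort 3 would not meet the cohort count, and no written condition of the gate would then prevent the opening of the 2 to under 6 year group.

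The plan handles the adult and adolescent step differently. Section 4.1 starts Cohort 2 only if no cipargamin arm in Cohort 1 has met the stopping criteria. For Cohort 2, Table 4-1 allows a dose change either on PK data or because an arm met those criteria. The paediatric steps have no such link.

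**Working it through.** **Inputs.** Counts come from Protocol Table 3-1 and SAP Table 2-14, and sizes from Protocol Section 12.8.2. The documents give no expected event rate, so I use a range. The 40% rate is the one that Section 12.8.2 uses for a group of six.

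**Formula.** P(at least r events among n) = sum over k = r to n of C(n,k) p^k (1-p)^(n-k).

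**Step 1: reproduce the plan's own figures.**

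| n | r | Stated | Computed |
|---|---|---|---|
| 6 | 2 | above 75% at 40%; below 20% at 10% | 76.7%; 11.4% |
| 14 | 2 | about 80% at 20%; below 20% at 5% | 80.2%; 15.3% |
| 20 | 3 | about 80% at 20%; below 20% at 7% | 79.4%; 16.1% |
| 38 | 6 (SAP 3.2) | about 80% at 20%; below 20% at 10% | 80.0%; 17.5% |
| 38 | 9 (Protocol 12.8.2) | about 80% at 20%; below 20% at 10% | 34.5%; 1.1% |
| 116 | 14 | above 80% at 15%; below 20% at 9% | 84.5%; 16.0% |

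All rows reproduce except the Protocol's 9 events for n = 38. That figure disagrees with its own Table 3-1 and with the SAP, both of which use 6.

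**Step 2: apply the Cohort 3/4 count to a lead-in of six.** P(6 of 6) = p^6.

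| True rate | Count of 6 met within six | For scale: 2 or more of six |
|---|---|---|
| 10% | 0.0001% | 11.4% |
| 20% | 0.006% | 34.5% |
| 30% | 0.07% | 58.0% |
| 40% | 0.41% | 76.7% |
| 50% | 1.6% | 89.1% |
| 80% | 26.2% | 99.8% |

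An 80% chance of meeting the count needs p = 0.8^(1/6) = 0.963. With five or fewer children the chance is zero. At 40%, the expected number treated up to the sixth event is 6/0.4 = 15, and the chance of still having five or fewer events after 15 children is 40.3%. In Cohort 5 (count 3), the chance within six at 40% is 45.6%.

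The last column shows how the plan's own row for six participants behaves. It is a yardstick, not a proposed rule.

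**Step 3: does the study-wide count of 14 act sooner?** If no cohort count was met earlier, at most 1 + 1 = 2 events carry into Cohort 3, so 14 - 2 = 12 more are needed. At most 1 + 1 + 5 = 7 stand before or alongside Cohort 4, so 14 - 7 = 7 more are needed. Both exceed six. A sixth event in Cohort 3 while it is still recruiting could pause the study during the Cohort 4 lead-in, but that is the Cohort 3 count acting.

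**Step 4: set the sections side by side.** Section 4.5 claims safety reviews between cohorts. Between Cohorts 2 and 3 there is the interim assessment with DMC review. Between Cohorts 4 and 5 there is a DMC meeting. Between Cohorts 3 and 4 there is only the PK check.

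**The case against.** The strongest reply is that the numeric counts are not the only protection. The sponsor monitors safety continuously and extra DMC meetings can be called (Section 3). An arm can be put on hold as needed (Section 4.5). Reviewers independent of the trial team see unblinded safety data (Section 6.4). A different dose can be considered if the dose looks unsuitable in a cohort's first few participants (Section 9.1.1.1). The DMC may recommend dose or age adjustment, or stopping a cohort (Section 12.7). SAP 1.1 records that the DMC endorsed the Cohort 3 and 4 dosing schedule. The lead-in's stated aim is also to confirm exposure within a range judged safe from Cohorts 1 and 2. The DMC charter is a separate document, and part of the dose rationale is redacted.

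Much of this stands, and it rules out three stronger readings. A reader might infer that 6 events is the only written safety trigger, or that all six children must have an event before any pause. The study-wide 14 also exists, there is a separate count for rescue use, and discretion can act at any time. A reader might infer that an unsafe dose would necessarily pass; with these safeguards in place, that does not follow. A reader might also infer that the six-participant row was meant for the lead-ins. The documents do not say so. That row matches Cohort 1, which has milder disease and older participants, and the lead-in may hold fewer than six.

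The reply does not close the gap. None of these measures has a threshold or is tied to the release decision. The independent reviewers' stated purpose is decisions on the stopping criteria, whose cohort count here is 6.

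**Conclusion.** The point holds in this form: the release decision in Cohorts 3-5 names no safety condition, and the cohort-level count for Cohorts 3 and 4 cannot act within the lead-in short of six events in six children. At a 40% event rate that is a 0.4% chance, and at lower rates less. Section 4.5 is not borne out at the Cohort 3-to-4 step, where the gap is sharpest. Cohort 5 is better covered, with a count of 3 and a DMC meeting before it opens, although release of its remaining recruitment still names PK only.

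The figures assume independent events at a common rate and a full lead-in of six. The statement about the count of 14 assumes planned cohort sizes and no earlier pause and restart. After a restart, or with the additional participants that Table 4-1 allows, it could act sooner. The charter may contain a lead-in review, but the protocol and SAP do not point to one.

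**What to change.** Reconcile Protocol Sections 3, 4.4 and 4.5, Tables 3-1 and 4-1 and SAP Table 2-14 so that:

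- the lead-in decision in Cohorts 3-5 includes a safety review by the existing unblinded reviewers, with the existing DMC as needed, alongside the PK check;
- the documents state which safety criterion governs the lead-in group, including when fewer than six children are treated, and how much follow-up the review needs. The sponsor and DMC choose these.

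In the same amendment, settle two inconsistencies. Section 3 says in one sentence that recruitment will be paused when the criteria are met, and in another that the study may be paused. Section 12.8.2 uses 9 events for n = 38, where Table 3-1 and SAP 3.2 use 6.

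**Cost.** The text changes are small and need no new staff or committee. Release is delayed by a short review, and longer if late events such as delayed hemolysis are to be seen first. There will be some unneeded ad hoc DMC reviews, at a frequency that depends on the criterion and on background mortality, because deaths from any cause count. For scale only, the existing six-participant row would flag 11.4% of full lead-ins at a true 10% rate, or 1 - (1 - 0.1143)^3 = 30.5% for at least one of three. At 20% it would flag 34.5% of lead-ins.
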